## LIST OF ABBREVIATIONS

AE	adverse event
AED	antiepileptic drug(s)
ALP	alkaline phosphatase
ALT	alanine aminotransferase
AST	aspartate aminotransferase
AV	atrioventricular
bid	twice daily
BMI	body mass index
BP	blood pressure
BRIEF ®	Behavior Rating Inventory of Executive Function ®
BRIEF-P ®	Behavior Rating Inventory of Executive Function-Preschool Version ®
CBCL	Child Behavior Checklist
CDMS	clinical data management system
CPM	Clinical Project Manager
CRO	contract research organization
C-SSRS	Columbia-Suicide Severity Rating Scale
ECG	electrocardiogram
eCRF	electronic Case Report form
EDC	electronic data capture
EI-AED	enzyme-inducing antiepileptic drug
EQ-5D-3L	3-level EuroQol-5 Dimension Quality of Life Assessment
ES	Enrolled Set
ET	Early Termination
GCP	Good Clinical Practice
HRQoL	health-related quality of life
ICH	International Council for Harmonisation
IEC	Independent Ethics Committee
IGE	idiopathic generalized epilepsy
ILAE	International League Against Epilepsy
IMP	investigational medicinal product

---

IRB	Institutional Review Board
IRT	interactive response technology
iv	intravenous
LCM	lacosamide
LFT	liver function test
MAO-A	monoamine oxidase A
MAP	managed access program
PDILI	potential drug-induced liver injury
PedsQL™	Pediatric Quality of Life Inventory
PGTCS	primary generalized tonic-clonic seizure(s)
PK	pharmacokinetic
PS	Patient Safety
QOLIE-31-P	Patient Weighted Quality of Life in Epilepsy Inventory-Form 31
SAE	serious adverse event
SAP	Statistical Analysis Plan
SD	standard deviation
SFU	Safety Follow Up
SOP	Standard Operating Procedure
SS	Safety Set
TEAEs	treatment-emergent adverse events
TMF	trial master file
ULN	upper limit of normal
VAS	visual analogue scale

## 1 SUMMARY

This Phase 3, multicenter, open-label extension study is designed to assess the long-term safety and efficacy of oral lacosamide (LCM, VIMPAT®; SPM 927; previously referred to as harkoseride; (R)-2-acetamido-N-benzyl-3-methoxypropionamide, ADD 234037) as an adjunctive therapy for uncontrolled primary generalized tonic-clonic seizures (PGTCS) in subjects  $\geq 4$  years of age with idiopathic generalized epilepsy (IGE). This study will enroll subjects who have completed the LCM SP0982 study. In addition, subjects who completed the SP0982 Prospective Baseline Period and met all entry criteria except the minimum PGTCS criteria required for randomization into SP0982 may choose to enter EP0012 (eligible Baseline failures and completers are defined in Section 5.1). It is estimated that up to 250 subjects across approximately 150 to 180 sites will be enrolled in EP0012.

Once 125 subjects have had a second PGTCS in SP0982, that study will have met its protocol-defined stopping criteria and all subjects will transition into EP0012 or taper off study medication. Subjects who completed SP0982 will start at Visit 1 on a dose of LCM 10mg/kg/day for pediatric subjects weighing  $< 30$ kg, LCM 8mg/kg/day for pediatric subjects weighing  $\geq 30$ kg to  $< 50$ kg, and LCM 400mg/day (200mg twice daily [bid]) for adult subjects ( $\geq 18$  years of age) or pediatric subjects weighing  $\geq 50$ kg. Subjects who are eligible Baseline failures from SP0982 will start at Visit 1 on a dose of LCM 2mg/kg/day for pediatric subjects weighing  $< 50$ kg, and LCM 100mg/day (50mg bid) for adult subjects ( $\geq 18$  years of age) or pediatric subjects weighing  $\geq 50$ kg.

Baseline failures are required to complete Week 1 of dosing before LCM dosing flexibility based on tolerability is allowed. Investigators will assess whether a subject would tolerate a further LCM dose increase or whether a subject should hold the dose for a longer duration. There is no limit to the number of back titration steps or dose holds allowed and all are at the Investigator's discretion; however, subjects must achieve the minimum LCM target dose of 4mg/kg/day (oral solution) or 200mg/day (tablets) within 14 days after Visit 1.

At any time during the course of the study if it becomes apparent that a subject is unable to attain at least this minimum dose of 4mg/kg/day (oral solution) or 200mg/day (tablets), then the subject must enter the Taper Period and be withdrawn from the study.

During EP0012, investigators will be allowed to increase or decrease the dose of LCM to optimize tolerability and seizure reduction. Lacosamide doses may be increased or decreased in steps of no more than 2mg/kg/day (oral solution) or 100mg/day (tablets). Subjects must remain on the dose for  $\geq 7$  days before a subsequent dose escalation.

EP0012 will consist of a Treatment Period, an up to 4-week Taper Period, and a 30-day Safety Follow-Up Period. During the Treatment Period, Visit 2 will occur 2 weeks after Visit 1, and Visit 3 will occur 4 weeks later (Week 6). Clinical visits will then occur every 8 weeks for the first year, and every 16 weeks in the second year. For subjects who continue in the study after Year 2, visits will occur every 24 weeks thereafter until the end of the study. From Year 2 (Visit 11) to 3 onwards, pediatric subjects weighing  $< 50$ kg will return to the clinic for an additional Dispensation Visit 12 weeks after each 24-weekly visit, for the dispensation of LCM solution; LCM usage will be reviewed and empty LCM bottles will be returned.

A telephone contact will occur every 8 weeks if no clinic visit is scheduled. The study duration and the total number of clinic visits will vary for each subject. Treatment will continue until LCM is approved for use in the subject's country for the treatment of PGTCs in subjects with IGE, or until UCB has determined that the clinical development program for the indication will be formally discontinued, or until UCB decides to close the study.

At the completion of the study, investigators should discuss treatment options with the subject and/or their parent(s)/legal representative(s) to best manage the subject's epilepsy. Taper of LCM may not be required for some subjects who complete the study depending on the treatment option selected by the investigator in consultation with the subject and/or their parent(s)/legal representative(s).

The primary study objective is to assess the safety and tolerability of LCM as an adjunctive therapy for uncontrolled PGTCs in subjects with IGE during long-term exposure. Secondary objectives are to assess the efficacy of adjunctive LCM therapy during long-term exposure for the treatment of uncontrolled PGTCs in subjects with IGE, and to allow subjects who have completed SP0982 and eligible Baseline failures from SP0982 to receive LCM.

The primary safety variables are adverse events (AEs), subject withdrawals due to AEs, incidence of new seizure types, and increase in absence seizure days per 28 days or myoclonic seizure days per 28 days during the Treatment Period. Secondary safety variables are percentage of treatment-emergent marked abnormalities in hematology and chemistry parameters; percentage of treatment-emergent marked abnormalities in 12-lead electrocardiograms (ECGs); and percentage of treatment-emergent marked abnormalities in vital sign measurements (ie, blood pressure [BP] and pulse rate). Other safety variables include changes in hematology, chemistry, and urinalysis parameters, changes in 12-lead ECGs, and changes in vital sign measurements (ie, BP and pulse rate), including height and weight and physical (including neurological) examination findings. In addition, for pediatric subjects <18 years of age, safety will be evaluated using behavioral assessments (Achenbach Child Behavior Checklist [CBCL]), and cognitive function assessments (Behavior Rating Inventory of Executive Function®/Behavior Rating Inventory of Executive Function-Preschool Version® [BRIEF®/BRIEF-P®]). The seizure efficacy variables are evaluations of seizure frequency, based on information included in subject diaries. The health outcome variables, including the Patient Weighted Quality of Life in Epilepsy Inventory-Form 31 (QOLIE-31-P), the Pediatric Quality of Life Inventory™ (PedsQL™), the 3-level EuroQol-5 Dimension Quality of Life Assessment (EQ-5D-3L), healthcare resource use, the number of working or school days lost by subjects due to epilepsy, and the number of days with help from a caregiver due to epilepsy will be assessed for the first 2 years of treatment.

## 2 INTRODUCTION

Epilepsy is the second most prevalent neurological disorder in the world. It is estimated to affect almost 70 million people worldwide (Ngugi et al, 2011). Epileptic seizures occur in the context of a wide range of epilepsy syndromes that may be of genetic, structural/metabolic, or unknown origin.

Generalized seizures are those in which the first clinical changes indicate initial involvement of both brain hemispheres. Consciousness typically is impaired and this impairment may be

the initial manifestation. Motor manifestations are typically bilateral. Generalized seizures typically occur with idiopathic generalized (genetic) or symptomatic generalized epilepsy syndromes. Idiopathic generalized epilepsy is a category of disorders defined by strict clinical and electroencephalogram features proposed by the International League Against Epilepsy (ILAE) classification of epileptic syndromes (ILAE, 1989). Clinical experience has shown that IGEs represent a heterogeneous condition in which many factors interact (such as age at onset, external factors, role of medications, and sleep) (Jallon and Latour, 2005). Idiopathic generalized epilepsies are assumed to have a genetic etiology and onset almost always occurs during childhood or adolescence, although there are exceptions; some patients develop these kinds of epilepsies after the second decade of life or, rarely, even later.

Treatment of PGTCS in IGE is complex because the patient population is heterogeneous, as PGTCS can occur as an isolated seizure type or in association with other generalized seizure types.

Although some forms of epilepsy may not require any treatment at all, most patients with epilepsy require appropriate pharmacological therapy (Perucca, 1996). In the past decade, several new options for the medical treatment of epilepsy have been introduced, including novel antiepileptic drugs (AEDs) and vagus nerve stimulation. The newer AEDs differ from older agents in several important ways, including mechanism of action, spectrum of activity, and pharmacokinetic (PK) characteristics (Herman and Pedley, 1998).

Between 15% and 40% of patients with generalized epilepsy remain refractory to therapy or do not tolerate the currently available AEDs used in this population (Bartolomei et al, 1997; Verrotti et al, 2007); some of these AEDs can induce serious, life threatening AEs (eg, aplastic anemia, rash, hepatic failure). Generalized tonic-clonic seizures may respond to drugs that aggravate typical absences and/or myoclonic jerks (Genton, 2000; Verrotti et al, 2007). Two IGE seizure types, typical absences and myoclonic seizures, are particularly prone to aggravation by certain AEDs (carbamazepine, vigabatrin, tiagabine, phenytoin, phenobarbital, and lamotrigine).

Lacosamide belongs to a novel class of functionalized amino acids that were specifically synthesized as anticonvulsive drug candidates. It has minimal protein binding and effect on cytochrome P450 enzyme system function (reducing the risk of drug-drug interactions), high oral bioavailability, and a half-life of approximately 13 hours (in adults), which allows a bid dose regimen. It also displays dose-proportional PK following administration over a range of doses up to 800mg in adults.

Lacosamide has been approved in the European Union (oral tablets, oral solution [syrup], and solution for intravenous [iv] infusion) as monotherapy or adjunctive therapy in the treatment of partial-onset seizures with or without secondary generalization in patients 4 years of age and older. Lacosamide has also been approved in the US (oral tablets, oral solution [syrup], and solution for iv infusion) as monotherapy or adjunctive therapy in the treatment of partial-onset seizures in patients 17 years of age and older. The safety and efficacy of LCM has also been evaluated in Phase 2/3 studies as adjunctive oral therapy in over 1300 adult subjects with partial-onset seizures. Excluding blinded ongoing studies and indications not currently pursued, as of the data cutoff of 31 Aug 2016, 4938 subjects have been exposed to LCM in the clinical development program.

Preliminary recent safety and PK data suggest that the exposure-response in pediatric and adult subjects treated with LCM will be similar. Lacosamide has been evaluated in 3 completed pediatric studies; 2 studies in subjects aged 1 month to 17 years, and in subjects with epilepsy  $\geq 4$  years to  $< 17$  years of age with uncontrolled partial-onset seizures. Subjects who completed the Maintenance Period were offered the opportunity to participate in the open-label extension study.

In addition, LCM is being evaluated in the following ongoing pediatric efficacy and safety studies:

- SP0967 (ages  $\geq 1$  month to  $< 4$  years) as adjunctive therapy in partial-onset seizures
- EP0034, Open-label extension study to SP0967 and SP0969
- SP0966 (ages  $\geq 1$  month to  $< 18$  years) as adjunctive therapy, exploratory study in subjects with epilepsy syndromes associated with generalized seizures

Further information on LCM nonclinical results, as well as the PK, efficacy, and safety profiles, can be obtained from the current version of the LCM Investigator's Brochure.

Considering the significant unmet medical need for new treatment options for patients with IGE and PGTCs, the efficacy and tolerability profiles for LCM were evaluated in a series of animal models followed by a Phase 2 pilot study of patients with IGE and uncontrolled PGTCs.

Lacosamide demonstrated significant seizure protection in animal models of seizures and epilepsy mimicking generalized epilepsy in humans. Of particular relevance for the PGTCs indication are the anticonvulsant properties of LCM treatment obtained against generalized tonic-clonic seizures induced by a maximal electroshock in both mice and rats, and sound stimulation in audiogenic seizure susceptible mice. In these models, LCM treatment significantly protected against generalized tonic-clonic seizures. The elevation of seizure threshold by LCM following iv infusion of pentylenetetrazol in mice may also be indicative of a potential efficacy against myoclonic seizures, where LCM treatment significantly delayed time to first myoclonic seizure. However, LCM had no protective effect in animal models of absence seizures and increased spike and wave discharges in the WAG/R and Genetic Absence Epilepsy Rats from Strasbourg models of absence epilepsy.

SP0961, the Phase 2, multicenter, open-label pilot study designed to assess the safety of adjunctive LCM (400mg/day) for uncontrolled PGTCs in subjects aged 16 to 65 years with IGE, is complete. The results of this pilot study showed reductions in PGTCs and myoclonic seizure frequencies, with a small reduction in absence seizure frequency. A minority of subjects (~10%) in SP0961 showed an increase in absence seizures (reported as treatment-emergent adverse events [TEAEs]) that, in this uncontrolled study, cannot be distinguished between the drug versus the natural course of the disease. The AE profile was similar to what has been observed with adjunctive LCM for the treatment of subjects with partial-onset seizures, with the exception of seizure-related AEs.

SP0982 is a Phase 3, double-blind, randomized, placebo-controlled, parallel-group, multicenter study designed to evaluate the efficacy and safety of LCM for uncontrolled PGTCs in subjects  $\geq 4$  years of age with IGE.

The current study (EP0012) will assess the long-term safety, tolerability, and efficacy of LCM and will enroll subjects who have completed SP0982 as well as eligible Baseline failures from SP0982. At the completion of the study, investigators should discuss treatment options with the subject and/or legal representative to best manage the subject's epilepsy.

### **3 STUDY OBJECTIVE(S)**

#### **3.1 Primary objective**

The primary objective is to assess the safety and tolerability of LCM as an adjunctive therapy for uncontrolled PGTCs in subjects with IGE during long-term exposure.

#### **3.2 Secondary objectives**

The secondary objectives are:

- To assess the efficacy of adjunctive LCM therapy during long-term exposure for the treatment of subjects with IGE experiencing uncontrolled PGTCs
- To allow subjects who have completed SP0982 and eligible Baseline failures from SP0982 to receive LCM

### **4 STUDY VARIABLES**

#### **4.1 Safety variables**

##### **4.1.1 Primary safety variables**

The primary safety variables are:

- The incidence of TEAEs over the duration of the Treatment Period.
- Subject withdrawals due to TEAEs
- Incidence of new appearance of absence and/or myoclonic seizures during the Treatment Period
- An increase of up to 25%, >25% to 50%, >50% to 75%, and >75% in days with absence seizures per 28 days compared to the Prospective Baseline
- An increase of up to 25%, >25% to 50%, >50% to 75%, and >75% in days with myoclonic seizures per 28 days compared to the Prospective Baseline
- At least 50% worsening in days with absence seizures
- At least 50% worsening in days with myoclonic seizures

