#### **4.2.2 Secondary efficacy variable**

The secondary efficacy variable is:

- Percent change in PGTCs frequency per 28 days from Combined Baseline, where Combined Baseline is defined as the combined 12-week Historical Baseline and 4-week Prospective Baseline periods immediately prior to randomization in the parent study (SP0982)

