#### **4.2.3 Other efficacy variables**

The other efficacy variables are:

- Change in days with myoclonic seizures per 28 days relative to the Prospective Baseline
- Percent change in days with myoclonic seizures per 28 days relative to the Prospective Baseline
- Change in days with absence seizures per 28 days relative to the Prospective Baseline
- Percent change in days with absence seizures per 28 days relative to the Prospective Baseline
- At least a 50% reduction in PGTCs frequency compared to the Combined Baseline
- At least a 50% reduction in myoclonic seizure days compared to the Prospective Baseline
- At least a 50% reduction in absence seizure days compared to the Prospective Baseline
- Seizure-free status (yes/no) for PGTCs
- Seizure-free status (yes/no) for all generalized seizure types
- Change from Baseline in QOLIE-31-P subscale (Seizure Worry, Daily Activities/Social Functioning, Energy/Fatigue, Emotional Well-being, Mental Activity/Cognitive Functioning, Overall Quality of Life, and Medication Effects) and total scores in subjects

≥18 years of age or change from Baseline in the PedsQL subscale (Physical Functioning, Emotional Functioning, Social Functioning, and School Functioning) and total scores in subjects <18 years of age for the first 2 years of treatment

- Change from Baseline in the EQ-5D-3L visual analogue scale (VAS) score and change in utility as converted from the 5 dimensions (for subjects ≥12 years of age) for the first two years of treatment
- Healthcare resource use: medical procedures, hospitalizations, and healthcare provider visits for the first 2 years of treatment.
- Number of working or school days lost by subject due to epilepsy for the first two years of treatment.
- Number of days with help from a caregiver due to epilepsy for the first two years of treatment

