### **9.1.2 Absence and myoclonic seizures**

In the subject diary, the following information will be recorded:

- Seizure type
- Number of seizures to be recorded although for the purpose of data analysis, only the number of days with seizure will be analyzed.

Investigators should advise subjects and/or caregivers about the importance of reporting absence and myoclonic seizures.

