### **10.2 New seizure types, increase in days with and worsening of days with absence or myoclonic seizures**

Incidence of new seizure types, increase in absence seizure days or myoclonic seizure days per 28 days during the Treatment Period, and 50% worsening in days with absence seizures or myoclonic seizures per 28 days during the Treatment Period will be assessed using the seizure count information recorded on the subject diaries (see Section 9.1).

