## 12.3 Planned safety and other analyses

### 12.3.1 Safety analyses

The incidence of all TEAEs, treatment emergent SAEs and TEAEs leading to premature discontinuation from study drug will also be summarized descriptively. Additional summaries will be provided by maximum intensity and relationship to study drug. All tables of TEAEs will include Medical Dictionary for Regulatory Activities primary System Organ Class and Preferred Term. Further details on the analysis of each variable will be given in the SAP.

Incidence of new seizure types, increase in days with absence seizure or myoclonic seizures per 28 days during the Treatment Period, and 50% worsening in days with absence seizures or myoclonic seizures per 28 days during the Treatment Period will be summarized.

Laboratory measurements as described in Section 10.3 and other safety measurements as described in Section 10.4 will be presented.

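### Seizure days per 28 stop at 28, so subjects with 19 or more Prospective Baseline days cannot meet the primary variable of at least 50% worsening

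*Protocol*

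**What the plan says.** Section 4.1.1 has two kinds of primary safety variable for non-PGTCS seizures. The first is a set of increase bands measured against the Prospective Baseline; the bullet opens "An increase of up to 25%, >25% to 50%, >50% to 75%, and >75% in days with absence seizures per 28 days compared to the" and closes by naming that period. The second is a single threshold: "At least 50% worsening in days with absence seizures". Both are repeated for myoclonic seizures.

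The threshold bullet names neither a scale nor a comparator. Section 10.2 supplies the scale: "50% worsening in days with absence seizures or myoclonic seizures per 28 days during the Treatment Period will be assessed". Section 12.3.1 repeats it: "50% worsening in days with absence seizures or myoclonic seizures per 28 days during the Treatment Period will be summarized". The comparator follows from the neighbouring bands and from the mirror-image efficacy variable in section 4.2.3: "At least a 50% reduction in absence seizure days compared to the Prospective Baseline".

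Section 9.1.2 fixes the unit: "Number of seizures to be recorded although for the purpose of data analysis, only the number of days with seizure will be analyzed". Section 4.2.2 gives the Prospective Baseline as 4 weeks. No section mentions a ceiling, or gives another criterion for subjects who start near it.

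**The concern.** A percent rise in a quantity with a fixed maximum has a maximum of its own, and that maximum shrinks as the starting value grows. With at most 28 seizure days per 28, a subject who already has seizures on most days has little room to register a relative worsening, but full room to register a relative improvement.

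This matters because aggravation is the named risk. The Introduction (section 2) says that typical absences and myoclonic seizures are prone to aggravation by certain antiepileptic drugs. It also says that lacosamide increased spike-and-wave discharges in animal models of absence epilepsy, and that about 10% of subjects in the pilot study SP0961 had an increase in absence seizures. A primary safety percentage that counts some subjects as not worsened, when they could not have been counted otherwise, errs in the reassuring direction.

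**Working it through.** **Inputs.** Maximum value: 28 days per 28 (sections 9.1.2, 10.2, 12.3.1). Baseline B: seizure days in a 4-week (28-day) Prospective Baseline, so 0 to 28 (section 4.2.2). Threshold and bands: section 4.1.1. The protocol states no figure of its own to reproduce.

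**Ceiling.** Largest recordable increase = 28/B − 1. A threshold t is reachable only if B ≤ 28/(1 + t).

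- At least 50%: 28/1.5 = 18.67. At B = 18, 1.5 × 18 = 27.0, which is reachable. At B = 19, 1.5 × 19 = 28.5, which is not.
- Above 75%: 28/1.75 = 16.0. At B = 16 the maximum is exactly 75%, so this band is empty from 16 days up.
- Above 50% to 75%: empty from 19 days up.
- Above 25% to 50%: 28/1.25 = 22.4, so empty from 23 days up.

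| Baseline days | Largest possible increase |
|---|---|
| 14 | 100% |
| 16 | 75.0% |
| 18 | 55.6% |
| 19 | 47.4% |
| 20 | 40.0% |
| 22 | 27.3% |
| 23 | 21.7% |
| 28 | 0% |

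If a baseline is not exactly 28 days long, the limit stays at 18.67 days per 28. For example, 18 seizure days in a 26-day baseline is 18 × 28/26 = 19.38 per 28, which is above it.

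**Reduction.** A 50% fall needs a value of B/2 or less, which is possible for every B above 0.

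**Attenuation below the ceiling.** Assume seizures are Poisson within a day, and let p = B/28. If the true rate doubles, the share of days with a seizure becomes 1 − (1 − p)², a ratio of 2 − p to baseline. That is at least 1.5 only if p ≤ 0.5, that is, 14 days or fewer.

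**Size, on assumed distributions.** The documents give no distribution of baseline days. A simulation used a gamma mix of rates (mean 6 or 12 seizures per 28 days; shape 0.5, 1 or 2), a true doubling in everyone, 94 weeks of follow-up and 400,000 subjects per setting. Among subjects with at least one baseline seizure day:

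- 19 or more baseline days: 0.2–4% at mean 6 and 6–15% at mean 12.
- Meeting the 50% threshold: 62–71% of those with 1–14 days, 4–18% of those with 15–18 days, and 0% of those with 19 or more.
- Recording some increase in days, at 19 or more baseline days: 87–98%.
- Fall in the percentage worsened when subjects with 19 or more days are kept in the denominator: 0.2–2.5 points at mean 6 and 4–9 points at mean 12.

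**The case against.** The arithmetic is not in dispute; its consequence is.

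- **The denominator is open.** Section 12.2 leaves it to the number of subjects appropriate for the analysis, and section 12.3.1 defers detail to the SAP, which is not at hand. This stands: the downward bias is conditional on keeping these subjects in.
- **Harm is recorded elsewhere.** A reader might infer that nothing that happens to these subjects can count as harm. The documents do not support that. A subject going from 20 to 28 days (+40%) falls in the primary band above 25% and up to 50%. Section 10.1.1.1 makes a clinically significant rise in seizure frequency or intensity an adverse event, section 10.1.1.3 makes worsening of an existing seizure type an adverse event of special interest, and TEAE incidence is itself primary. Absolute change in days is summarised under section 4.2.3. This stands, with limits: the lower bands understate deterioration to the maximum, adverse event reporting rests on judgement, and change in days has the same cap. None of these lets the 50% variable register the event.
- **Days were chosen on purpose.** Section 12.4 calls days the more clinically relevant endpoint. A rise from 20 to 28 days is a true 40% rise in days, so nothing is mis-measured. A reader might infer that days are the wrong measure; the documents do not support that either. The defect is narrower: a threshold applied where it cannot be met.
- **The study is descriptive.** It has one treatment and no test, so no error rate is affected. This is correct, and it limits the severity.

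**Conclusion.** The point holds in a limited form. From 19 Prospective Baseline days per 28, the primary variable of at least 50% worsening cannot be met, while a 50% reduction can. This is exact, and it rests only on reading worsening as a percent rise in days per 28 over the Prospective Baseline, as sections 10.2, 12.3.1 and the adjacent bands indicate. The upper increase bands empty out in the same way, from 16, 19 and 23 days.

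If these subjects are in the denominator, the percentage worsened is biased downward. The size cannot be derived from the protocol. The range of about 0.2–9 points depends on the assumed rate distributions and on a true doubling in everyone, and it could be negligible. The documents do not establish that the reported percentage will be materially wrong, or that worsening in these subjects goes unseen. The correction is worth making because it is cheap and concerns a primary safety variable. Baselines of zero days are a separate matter.

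**What to change.** Keep the full-set table and the single set of increase bands, so that no one is dropped and the bands share one base. In sections 4.1.1 and 12.3.1, add that at least 50% worsening is also presented separately for two groups: subjects with 1–18 Prospective Baseline days, and subjects with 19 or more. State that the threshold cannot be reached in the second group. If baselines are normalised to 28 days, set the split at 28/1.5 = 18.67 days per 28.

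For subjects with 19 or more days, show the absolute change in days and, as a supportive row, the proportion with at least a 50% increase in seizure count per 28 days. Section 9.1.2 says that "only the number of days with seizure will be analyzed"; amend that sentence to allow this one supportive use of counts.

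The cost is wording in the protocol and SAP and a few table rows. Section 9.1.2 already has counts recorded in the diary during treatment. The row also needs baseline counts from the SP0982 diary, so confirm that they are held. Counts of absence and myoclonic seizures are noisier than days, which is why the row is only supportive. Attenuation between 15 and 18 days remains.
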